4.1.4 Prior and Concomitant Therapy

The subjects will be required to have been on medical therapy for BPH for at least six months prior to undergoing PAE. Such medications include alpha blockers, 5-ARIs or combination therapy. The medication usage will be stopped by the 3 month visit in order to allow an adequate washout period for 5-ARI's prior to the 6 –month visit.

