4.1.10 Visit 5 - 3 Month Follow-Up

Subjects will return 90 +/- 14 days after PAE procedure to complete IPSS, and QOL questionnaires; to have Qmax and PVR measured; medication history questionnaires will be completed; and subjects will be evaluated for possible adverse events. It will be recorded if subjects are unable to hold medications at this time due to residual urinary symptoms. If an AE is suspected based on change in pain scores or functionality, an appropriate work-up will be performed.

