4.1.14 Criteria for Removal from Study

Subjects will be withdrawn from the study if a major complication occurs that prevents completion of PAE or the ability to complete the follow up visits.

Patients may also withdraw at any point at their discretion. Data will be included with an intent to treat analysis. Reasons for study withdrawal will be recorded.

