4.2.2 Effectiveness Assessments

Technical success will be defined as bilateral prostatic artery embolization. This will be determined during the procedure. Clinical success will be defined as an IPSS score reported at the 6-month visit that is equal to or less than the pre-PAE baseline score. The size of the prostate will be measured by MRI at 6-month follow-up visit. IPSS, QoL, PVR and Qmax will be measured at 3, 6 and 12-month follow-ups.

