8.0 STATISTICAL CONSIDERATIONS

8.1 Study Design/Study Endpoints

The primary study aim is to determine if PAE is as effective as medication (non-inferiority) in reducing urinary symptoms due to BPH at 6 months.

This will be a single arm, non-blinded study of PAE using HydroPearl Beads in a small population with BPH to assess a clinically significant reduction in medications at 6 months. After IRB approval of a written informed consent and over, approximately a 24 month duration, N=30 subjects will be recruited. Only subjects ≥ 40 years will be screened for study recruitment. Clinical procedures and evaluations will consist of a preoperative screening assessment to determine if the potential study subject meets the inclusion and exclusion criteria, enrollment, surgical procedure for prostatic artery embolization (PAE), and follow-up visits at 24 hours, 1 week, 3, 6, & 12 months. An MRI will be performed after the 6-month visit in those patients who underwent embolization to detect a change in prostatic volume and perfusion and to exclude complication.

The study will be stopped if there is greater than one major complication (Grade D, E or F) as defined by the Society of Interventional Radiology Classification System for Complications by Outcome (29).

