8.3 Data Analysis Plans

A patient will be considered an evaluable study subject evaluable for data analysis per the following criteria, a written informed consent was obtained, he meets the inclusion and exclusion criteria, and received the PAE study procedure. All subjects with 12-month follow-up data will be included for analysis even if some follow up data is incomplete. Every attempt will be made to ensure that there is as

little missing data as possible including reminder phone calls and follow-up phone calls, if a subject misses a visit.

The primary aim is to demonstrate non-inferiority of PAE compared to medication with respect to the outcome measure IPSS. We assumed a non-inferiority margin of 10%, in line with the FDA's recommendations, since similar prior non-inferiority trials were unavailable. The null hypothesis states that in the target population mean IPSS is at least 10% greater at 6 months post-treatment than at baseline (pre-treatment). The alternative hypothesis will be that the mean IPSS at 6 months is less than or equal to 10% greater than the mean IPSS at screening.

To address this hypothesis we will implement a random effects linear model, modeling IPSS score as a function of time and the indicator of whether medication had stopped by the time of the 3-month follow-up. We will include an R-side compound symmetric random effect to account for patient-level correlation. We will compute the predicted mean and standard deviation(SD) of IPSS at screening and 6 months; the difference of the predicted mean IPSS score, defined as the mean IPSS at 6 months minus the mean IPSS at screening; and the SD of this difference. Point estimates of these values will be reported along with 95% confidence intervals for the mean difference.

A non-inferiority p-value <0.05 testing whether the difference in the predicted mean at screening is at least 10% greater than the predicted mean of IPSS at screening will be considered evidence against the null hypothesis of inferiority of PAE, compared to treatment. A non-inferiority p-value >0.05 will be considered inconclusive evidence against inferiority.

As a sensitivity analysis for the primary aim, we will repeat the same model outlined above after removing patients from the analysis who were still taking medications at the 3-month follow-up. Point estimates, confidence intervals, and p-values will be compared against those obtained in the primary analysis.

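### The only sensitivity analysis removes men still on medication at 3 months, which selects those who did better, and no planned analysis scores continued medication as a failure of PAE

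*Combined protocol and SAP*

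**What the plan says.** Section 4.1.4 sets the expectation: "The medication usage will be stopped by the 3 month visit". Section 4.1.10 provides for men who do not manage this: "It will be recorded if subjects are unable to hold medications at this time due to residual urinary symptoms".

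The primary model in section 8.3 keeps every evaluable man, "modeling IPSS score as a function of time and the indicator of whether medication had stopped by the time of the 3-month follow-up". The one sensitivity analysis is then described as follows: "we will repeat the same model outlined above after removing patients from the analysis who were still taking medications at the 3-month follow-up". Its estimates, intervals and p-values are to be compared with the primary ones.

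Two other places bear on the point. Section 4.2.2 defines clinical success as an "IPSS score reported at the 6-month visit that is equal to or less than the pre-PAE baseline score", with no condition on medication. Section 8.1 gives as a purpose of the study "to assess a clinically significant reduction in medications at 6 months", but section 8.3 contains no analysis of medication use as an outcome.

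**The concern.** The trial asks whether PAE can stand in for medication. A man who still needs the drug because of symptoms has not had it replaced. Removing him conditions on something that happened after treatment and that belongs to the same domain as the endpoint, so those who remain are, on average, the better responders.

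The primary analysis has a different weakness. It uses such a man's score as measured, and that score may include drug benefit. Read as one value per patient, the stopped-by-3-months indicator is a main effect with no time interaction. It can shift a patient's overall level but does not take drug benefit out of the 6-month minus screening contrast. Neither the indicator nor the deletion rule sees a man who restarts between months 3 and 6.

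At stake is how the result is read. If the two analyses agree, a report could call the finding robust, although no analysis has asked how many men were both no worse than baseline and off medication.

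**Working it through.** **Inputs from section 8.2.** SD of IPSS 5.7 at both times; correlation 0.65; 30 men with 20% dropout, so 24 evaluable; alpha 0.025 (taken as one-sided; section 8.3 uses 0.05); PAE decrease 9.23; medication decrease 6.6.

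**The plan's own figure.** SD of change = 5.7 × √(2 × (1 − 0.65)) = 4.77. A paired t test with n = 24 and distance from the null (9.23 − 6.6) × 1.1 = 2.893 gives power 81.2%, as stated. That reading of the 10% margin is inferred from the match. It confirms the SD and n used below and does not otherwise affect this point.

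**Correlation between the 3- and 6-month changes.** Under compound symmetry, extending correlation ρ = 0.65 to all visit pairs, the covariance of the two changes is σ²(1 − ρ) and each variance is 2σ²(1 − ρ). The correlation is therefore 0.35 / 0.70 = 0.5.

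**Shift from deletion.** Suppose the worst fraction f at month 3 is deleted. The mean 6-month change then moves by about −[φ(z) / (1 − f)] × r × 4.77, where z cuts off the upper fraction f.
- f = 0.20: 0.280 / 0.80 = 0.350; 0.350 × 0.5 × 4.77 = 0.83 points toward PAE.
- f = 0.10: 0.1755 / 0.90 = 0.195; 0.195 × 0.5 × 4.77 = 0.46 points toward PAE.

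**False non-inferiority after deletion.** Simulated with the true off-drug change at a fixed margin and a one-sample t test at one-sided 0.025. With everyone's off-drug score the rate is 2.5%.

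| Men deleted | Correlation of changes | Mean shift | False non-inferiority |
|---|---|---|---|
| 2 of 24 | 0.5 | −0.4 | 6% |
| 3 of 30 | 0.5 | −0.4 | 7% |
| 5 of 24 | 0.5 | −0.8 | 12% |
| 6 of 30 | 0.5 | −0.8 | 14% |
| 6 of 30 | 0.65 (assumed) | −1.0 | 21% |
| 6 of 30 | 0.9 (assumed) | −1.5 | 42–43% |

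Setting the margin at 10% of an assumed baseline IPSS of 15 gives much the same: about 6% for 2 of 24 and 13% for 5 of 24. With noisier selection these fall to about 5% and 8%.

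**Shift in the primary analysis.** If a fraction f stays on a drug worth d points, the as-measured mean moves by −f × d. With f = 0.20: 0 if d = 0; 0.2 × 3.3 = 0.66; 0.2 × 6.6 = 1.32 points toward PAE. Whether the 6.6-point benefit holds after PAE is not documented.

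**Effect on clinical success.** In the baseline-15 simulation with 5 of 24 on medication and drug benefit from 0 to 6.6 points, success is 38–49% as section 4.2.2 defines it, 42–44% after deletion, and 33–35% if men on medication count as failures.

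**The case against.** The strongest reply is that the plan already pairs an all-treated analysis with something close to a per-protocol one. Section 4.1.14 adds "Data will be included with an intent to treat analysis", and section 4.1.15 keeps recorded data from men who withdraw. Much of this stands, and it rules out several stronger readings.

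- *That these men are never counted against PAE.* The primary analysis keeps them with their measured IPSS, and a man still symptomatic despite the drug raises the 6-month mean. What is missing is an analysis that scores the drug use itself.
- *That the deletion analysis can show nothing because both analyses always lean together.* The mechanisms differ: selection in one, drug masking in the other. With 6 of 30 men and correlation 0.5, deletion shifts the mean by −0.8, against −0.7 or −1.3 for the primary with a 3.3- or 6.6-point drug effect. At 6.6 points, deletion moves the estimate against PAE and nearer the truth. It is an incomplete check, not an empty one.
- *That every deleted man is a PAE failure.* Section 4.1.10 says only that inability to stop because of symptoms will be recorded. Section 8.3 deletes everyone still on medication, which can include men who are merely late in stopping. Selection is on 3-month drug status, not on 6-month IPSS.
- *That 21–43% is the expected error rate.* It needs change correlations of 0.65–0.9, above the 0.5 that the plan's own structure implies.
- *That any of these rates is the trial's false-positive rate.* The decision rests on the primary model.

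Clinical success is also not a listed outcome in section 2.3 and is not tested in section 8.3, so its definition is a secondary matter.

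**Conclusion.** The concern holds in limited form. The only robustness check selects on a post-PAE status linked to residual symptoms. The primary analysis may carry drug benefit in the same men. No planned analysis treats continued medication as failure, and section 4.2.2 counts such a man as a success if his IPSS is no higher than at baseline.

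The size depends on inputs the documents do not give: the share unable to stop, the strength of selection, and the baseline IPSS that turns 10% into points. The calculations also assume that the men deleted are exactly those with the worst 3-month change, except in the noisier-selection run. With the plan's correlation structure, false non-inferiority in the sensitivity analysis is about 6–8% with roughly 10% deleted and 12–14% with 20% deleted, against a nominal 2.5%. Deletion favours PAE, relative to the off-drug effect, in every setting examined. The change should be made, but the point does not invalidate the primary analysis.

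**What to change.** In section 8.3:

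1. Add an analysis of all treated men reporting the proportion with 6-month IPSS at or below baseline and off all BPH medication at 6 months, with a 95% CI. Take medication status from the Visit 6 questionnaire, which also catches restarts after month 3.
2. Report the number still on medication at 3 and at 6 months, with the reason recorded at Visit 5.
3. Keep the deletion analysis, labelled as describing men who stopped medication rather than as a test of robustness.
4. If an analysis assigning unfavourable scores is wanted, such as the worst observed change, call it a conservative bound. With 6 of 30 men affected and correlation 0.5 it moves the mean about 1.3 points against PAE.

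In section 4.2.2, align the definition of clinical success with item 1, or report both versions.

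The cost is SAP wording and a few lines of code, because the medication questionnaire is already scheduled at Visits 5 and 6. The reason for continuing is specified only at Visit 5, so having it at 6 months may need one added item at Visit 6. The reported success rate will be less favourable.

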2.3 Outcome Variable

2.3.1 Primary Study Outcome Variable

Reduction in IPSS at 6-month follow-up.

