4.1.11 Visit 6 - 6 Month Follow-Up

Subjects will return 180 +/- 14 days after PAE procedure to complete IPSS with QOL and medication history questionnaires and to have Qmax and PVR measured. The subjects will be evaluated for possible adverse events. If an AE is suspected based on change in pain scores or functionality, an appropriate work-up will be performed.

An MRI of the prostate will be acquired.

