4.1.13 Subject Compliance Monitoring

Study coordinators and physicians will inquire of the subjects to determine if they have escalated any current or initiated any new conservative therapies during the follow-up period.

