8.2 Sample Size Rationale

Prior studies have demonstrated larger decreases in IPSS scores using PAE, compared to medication alone. Abt found the mean decrease in IPSS to be 9.23 for PAE with standard deviations of IPSS scores being 5.7 at baseline and after treatment (18). Lepor found a decrease in IPSS attributable to medications of 6.6 (17).

We set a 10% non-inferiority margin and expect the correlation of IPSS scores between screening and 6-months to be high. Assuming a correlation of .65 we will have 81.2% power to test the non-inferiority hypothesis with an alpha of 0.025 for our 30 budgeted pairs, assuming 20% dropout (pairs=subjects given single subject study design).

Power calculations used PROC POWER, SAS, Version 9.4. This sample size is adequately large to address the study's primary aim with reasonably large power.

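### Section 8.3 fixes medication status at month 3, so a man who restarts a BPH drug before the month-6 primary IPSS is analysed as if he were off drug

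*Combined protocol and SAP*

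**What the plan says.** The primary outcome in 2.3.1 is "Reduction in IPSS at 6-month follow-up". Section 8.3 compares mean IPSS at month 6 with mean IPSS at screening, when every man is on a BPH drug. Section 4.1.4 requires the drugs to be "stopped by the 3 month visit in order to allow an adequate washout period" for 5-alpha reductase inhibitors ahead of the month-6 visit.

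Section 8.3 uses medication status in two places:

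- The primary model (IPSS on time, with a compound-symmetric within-patient covariance) has an indicator of whether medication had stopped by month 3.
- The only sensitivity analysis concerning medication repeats that model after "removing patients from the analysis who were still taking medications at the 3-month follow-up".

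Later drug use is asked about. At Visit 6 men return "to complete IPSS with QOL and medication history questionnaires", and the table in 4.3 shows the medication questionnaire at that visit. Section 4.1.13 has staff "determine if they have escalated any current or initiated any new conservative therapies during the follow-up period". Section 8.3 assigns none of this information to an analysis.

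**The concern.** The month-6 score is meant to show how men do after PAE once the drug has washed out, set against how they did on the drug. Both uses of medication status are tied to the start of the washout. Neither looks at the visit where the endpoint is measured.

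A man who stops by month 3 and restarts before Visit 6 is coded as stopped in the primary model and stays in the sensitivity analysis. His month-6 score includes whatever the drug does for him, and that benefit is credited to PAE. The error favours the hypothesis that the trial hopes to support. It grows if men restart because their symptoms remain. Section 4.1.10 already foresees men whose remaining symptoms prevent them from stopping at month 3.

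The existing sensitivity analysis has a related weakness. Men who cannot stop by month 3 are likely to be those in whom PAE worked least well, so leaving them out can also favour non-inferiority.

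**Working it through.** **Inputs from 8.2.** SD of IPSS 5.7; correlation 0.65; 30 pairs with 20% dropout, so 30 × 0.8 = 24 pairs; alpha 0.025; PAE decrease 9.23; "a decrease in IPSS attributable to medications of 6.6" points.

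**Assumed, because the documents give no figure.** Two of 24 men restart. The drug effect after PAE is 1, 3.3 (half of 6.6) or 6.6 points.

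**The plan's own figure.** SD of the difference = 5.7 × √(2 × (1 − 0.65)) = 4.77. Standard error at n = 24 = 4.77/√24 = 0.973. A one-sided paired t-test at 0.025 has 81.2% power, as stated in 8.2, when the true mean lies 1.10 × (9.23 − 6.6) = 2.893 points from the margin. That distance is inferred; 8.2 does not state it.

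**Shift in the mean.** If k of n men restart and each gains e points, the month-6 mean falls by e × k/n:

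- 1 × 2/24 = 0.08
- 3.3 × 2/24 = 0.275
- 6.6 × 2/24 = 0.55

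Shifting every man by the mean amount would give 7.8% false non-inferiority for 0.55 points. That is too high for random restarts, because a drug effect in only two men also widens the spread of the differences. The table simulates the men individually.

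**Simulation.** 200,000 trials, 24 pairs, one-sided paired t-test at 0.025, margin treated as fixed, true off-drug change exactly at the margin. Without restarts the rate is 2.5%. With two restarters:

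| Drug effect | Restart at random | Partly selected for poor change | Two worst changes |
|---|---|---|---|
| 1 point | 2.9% | not run | 3.4% |
| 3.3 points | 4.3% | 5.7% | 6.5% |
| 6.6 points | 6.0% | 10.0% | 12.6% |

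With 3.3 to 6.6 points, one random restarter gives 3.3–3.9% and four give 6.9–13.0%. Holding scores to 0–35, with assumed screening means of 15, 19 and 23, leaves two restarters at 4.3–6.9% (random) and 6.7–14.4% (worst), against 2.5–2.9% with none.

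Section 8.3 sets "A non-inferiority p-value <0.05" without saying whether it is one-sided. If it is, the 5.0% base rises to 8.0–11.2% (random) and 11.0–19.4% (worst) for 3.3 to 6.6 points.

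**Would excluding drug users solve it?** Not if they are selected for poor change. Excluding two of 24 men gives 2.5% when they are random, 8.5% when partly selected and 14.3% when they are the two worst. The same reasoning applies to the plan's month-3 exclusion.

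**Would updating the indicator solve it?** No. It is constant within a man and has no interaction with time. In 20 simulated data sets each, raising the men coded as not stopped from three to five left the month-6 contrast unchanged with complete data. With 6 of 30 men missing month 6, it moved by at most 0.10 points.

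**Would adding the drug effect back solve it?** If the added value equals the true effect, the rate returns to 2.5% in every case. Adding 6.6 when the truth is 3.3 gives 1.2% (random) or 0.7% (worst). Adding 3.3 when the truth is 6.6 gives 4.3% or 6.5%.

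**The case against.** The strongest reply is that the plan accepts on-drug scores. Section 8.3 keeps men who could not stop by month 3 in the primary analysis, and 4.1.14 mentions intent to treat. On that view this is a treatment-policy comparison with one sensitivity analysis attached. Part of this stands: the primary analysis need not change. But the intent-to-treat sentence sits under withdrawal and sets no rule for restarted drugs. The sensitivity analysis also shows that the authors regard drug use as able to distort the contrast.

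The second reply is that the size is assumed, and this stands. The 6.6 points are a published decrease with medication. Carrying the whole of it over to embolized men who restart within about three months is an upper bound. The truth is also placed exactly at the margin. If PAE is better by 9.23 − 6.6 = 2.63 points and the margin is 1.9 (assumed screening mean 19), non-inferiority is declared in 99.4% of trials without restarts and 99.8% with two restarters at 6.6 points. Under the plan's own expectation the conclusion hardly moves.

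Three stronger readings are tempting, and the documents do not support them:

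- A reader might infer that the exclusion analysis is the only use of medication status. It is not, because the primary model carries the month-3 indicator.
- A reader might infer that the error rate will reach the worst-case figures. Nothing in the documents gives a restart rate.
- A reader might take the aim in 8.1, "to assess a clinically significant reduction in medications at 6 months", as a promised month-6 drug analysis. It matches no outcome in 2.3 and is a separate inconsistency. Likewise, 4.1.13 speaks of conservative therapies and does not name BPH drugs.

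**Conclusion.** The gap is real and modest. No planned analysis handles a BPH drug restarted between month 3 and Visit 6, although medication history is taken at Visit 6. The bias runs towards non-inferiority, and the one existing check can lean the same way. The defect lies in the analysis plan and not in the schedule of data collection.

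For two random restarters of 24 at one-sided 0.025, about 3% to 6% false non-inferiority in place of 2.5% is a fair illustration, and more if the restarters are the men who did worst. This rests on an assumed restart rate, an assumed drug effect of 1 to 6.6 points, and a truth at the margin. It does not show that the trial's conclusion will be wrong. It shows that, as planned, no analysis would reveal whether the conclusion depends on restarted drugs. The change should be made before results are known.

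**What to change.** In 8.3:

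1. Define month-6 medication status (any BPH drug) from the Visit 6 medication questionnaire.
2. Report how many men are on a BPH drug at month 3 and at month 6.
3. Add one pre-specified sensitivity analysis that keeps every man. For any man on a BPH drug at month 6, whether he never stopped or restarted, add an assumed drug effect to his month-6 IPSS (for example 3.3 and then 6.6 points, capped at 35) and repeat the same test.
4. State that if non-inferiority holds only without this adjustment, the conclusion depends on the assumed drug effect.
5. Leave the primary analysis unchanged, and say that the month-3 exclusion analysis is open to selection bias.

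The cost is some wording and one model run at two values. No new visit or form is needed, but the Visit 6 questionnaire, whose content is not in the document, must record current use.

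The adjustment is a fixed assumed value, so it carries no uncertainty of its own. With two restarters and a true effect of 3.3, the 6.6-point version is conservative: power falls from about 81% to 72% (random) or 65% (two worst). The 3.3-point version corrects too little if the true effect is 6.6. Reporting both brackets the answer for true effects between those values. The sample size and the primary test are untouched.

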2.2 Secondary Objectives

The secondary aims are to determine if PAE will result in less adverse events compared to medication in individual patients and to determine if self assessed quality of life is better on medication or after PAE.

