2.3.2 Secondary Study Outcome Variable

1. Improvement of QoL score at 6 months
2. Improvement of uroflowmetry (Qmax, PVR) at 6 months
3. Reduction of prostate volume at 6 months
4. Percentage of prostate infarcted at 6 months
5. Incidence of adverse events at 3 months

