4.1.6 Screening Visit (Visit 1)

If a patient qualifies to be a subject in the study based on the inclusion and exclusion criteria listed in section 3.1 and 3.2, the study coordinator will be notified. The coordinator will review the study with the patient and obtain written informed consent. Once the subject is enrolled in the study, he will be seen by one of the co-investigators in either the IR or Urology clinics at one of the study sites. The procedure will be again described to the patient and any questions will be answered. International Prostate Symptoms Survey (IPSS) with Quality of Life (QOL) questionnaires and Qmax and PVR measurements will be obtained if not completed in the prior 3 months during the pre-study work-up. Study specific questionnaires to assess medication usage will also be completed. A MRI of the pelvis with and without contrast will be ordered and obtained prior to visit 2 for baseline evaluation of the prostate unless the patient has one from the prior 6 months. If the patient had a contrast enhanced MRI of the pelvis within the past 6 months, this MRI will be used.

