4.1.7 Visit 2 - PAE Procedure

PAE procedure will be performed as described in part 4.1.2 above within 8 weeks of Visit 1. Subjects will be given a pager number to reach a physician (24 hours a day) to report any adverse symptoms and receive medical advice.

Patients will be asked medication history questionnaire at this visit prior to the procedure.

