4.3 Time and Events Table

	Visit 1 (Screening)	Visit 2 (Procedure)	Visit 3 (1 Day)	Visit 4 (1 week)	Visit 5 (3 month)	Visit 6 (6 Month)	Visit 7 (12 month)
Informed Consent	X						
MRI	X					X	
PAE procedure		X					
IPSS w/QOL	X				X	X	X
Qmax	X				X	X	X
PVR	X				X	X	X
Medication History Questionnaire	X	X			X	X	
AE Assessment			X	X	X	X	

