To address the secondary aim, we will tabulate the proportion of patients AEs pre- and post-PAE, comparing the proportion using McNemar's test. A p-value <0.05 for McNemar's test will be considered evidence that the proportion of AE's differs for medication, compared to PAE. A p-value >0.05 will be considered inconclusive. We will assume that the adverse events that occur following PAE will be attributed to the procedure and not medication.

We will present the percentage of prostate infarcted at 6 months and the incidence of minor complications at 1 month descriptively, and calculate 95% confidence intervals. Post-acquisition segmentation software will be used to measure infarct volume.

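### The paired adverse-event comparison of PAE with medication has no adverse-event assessment scheduled before PAE, and its time windows are not stated

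*Combined protocol and SAP*

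**What the plan says.** Section 2.2 sets the aim: to "determine if PAE will result in less adverse events compared to medication in individual patients". Section 8.3 gives the only test of it. The plan states "we will tabulate the proportion of patients AEs pre- and post-PAE", names McNemar's test, and takes p<0.05 as evidence that the proportion differs between medication and PAE. It adds: "We will assume that the adverse events that occur following PAE will be attributed to the procedure and not medication".

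On data collection:
- In the 4.3 table, the row "AE Assessment" is marked at Visits 3, 4, 5 and 6 (1 day, 1 week, 3 months, 6 months). It is not marked at Visit 1 (screening) or Visit 2 (procedure).
- At Visit 1 (4.1.6): "Study specific questionnaires to assess medication usage will also be completed". At Visit 2 (4.1.7): "Patients will be asked medication history questionnaire at this visit prior to the procedure".
- Appendix 12.2 is a symptom checklist with a one-month recall. No visit is named for it.

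On timing, section 2.3.2 lists "Incidence of adverse events at 3 months", and section 8.3 separately plans to report the "incidence of minor complications at 1 month descriptively". Section 4.1.4 has BPH medication stopped by the 3-month visit. Section 4.1.10 provides for recording men who cannot stop by then.

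**The concern.** A paired test of adverse events on medication against adverse events after PAE depends on a baseline reading taken while each man is on his drug. If sites follow the schedule as printed, that reading is never taken, and afterwards it can only be recalled. The background (1.2) makes drug side effects the reason for considering PAE as first-line treatment, so the loss falls on a stated aim.

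A second, smaller matter is what the after value represents. No window is given for either half of the pair. If the post-PAE window overlaps continuing medication, the comparison is partly medication against medication plus PAE.

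**Working it through.** **No figure to reproduce.** The plan gives no power, adverse-event rate or discordance for this test. The 81.2% power in section 8.2 is for IPSS.

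**Step 1. Where could a pre-PAE value come from?**
- 4.3 table: adverse-event assessment at 0 of 2 visits up to PAE and at 4 of 5 after it.
- 4.1.6 and 4.1.7: medication usage or history only. The form is not reproduced, and it is a separate row from adverse-event assessment in 4.3.
- Sections 7.2 and 7.3.1: non-serious events are recorded from day 1 of study treatment. Before treatment, only serious events caused by a protocol-mandated intervention are collected. Section 7 is headed for drugs and contrast agents, so this supports the point less firmly than the 4.3 table does.
- Appendix 12.2: lists all six drug side effects named in 1.2, so it would suit a baseline, but it has no visit.

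No source is planned.

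**Step 2. What would a one-month post window cover?** Take one month as 30 days.
- Visit 5 is day 90 ± 14, that is day 76 to 104. The window starts at the earliest on day 76 − 30 = 46. Medication may continue to this visit, so the window can lie wholly on drug.
- Visit 6 is day 180 ± 14, earliest day 166. The window starts at the earliest on day 166 − 30 = 136, which is 136 − 104 = 32 days after the latest planned stop. Men who could not stop are still on drug, and the documents do not show that 32 days clears every drug effect.
- Both windows miss the first weeks, when section 4.1.9 expects most complications to appear. Visit 6 misses more.

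**Step 3. Direction of the overlap (illustration only).** Let B be the share of men with a drug symptom at baseline (assumed), K the share of those still reporting it after PAE (assumed), and N the share with a new PAE event. Then:
- P(symptom before only) = B(1−K)(1−N)
- P(symptom after only) = (1−B)N

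From 5.4, rectal pain and/or dysuria is 9.1% and hematuria 4.4%. The 12.2 form lists dysuria and blood in urine, so N = 1 − 0.909 × 0.956 = 0.131 if independent. The range is 0.044 (none of the 9.1% is dysuria) to 0.135 (no overlap). These are rates over follow-up, so a one-month window would catch fewer.

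Chance of a significant result favouring PAE, exact two-sided test at 0.05, n=30:

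| B | N | K=0 | K=25% | K=50% | K=100% |
|---|---|---|---|---|---|
| 0.3 | 0.131 | 24% | 10% | 2% | 0% |
| 0.5 | 0.131 | 82% | 55% | 22% | 0% |
| 0.7 | 0.131 | 99% | 94% | 65% | 0% |
| 0.5 | 0.044 | 98% | 89% | 56% | 0% |

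With 24 men (20% dropout from 30), the B=0.5, N=0.131 row becomes 70, 43, 15 and 0%. The direction is the same throughout. The size depends on B and K, which the documents do not give.

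**Step 4. Would judging relatedness after PAE solve it?** Suppose any symptom counts before PAE but only procedure-related ones count after, and every baseline symptom persists. With B=0.5 and N=0.131, P(before only) = 0.5 × 0.869 = 0.4345 and P(after only) = 0.5 × 0.131 = 0.0655. These are the K=0 cells, so the test favours PAE in 82% of trials of 30 men although no symptom resolved. One-sided attribution is worse than none.

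**The case against.** The best defence is that the baseline was intended and one mark is missing. Section 4.1.6 speaks of study-specific questionnaires in the plural. The medication history form is given at Visits 1, 2, 5 and 6, which is a before-and-after pattern. The 12.2 form fits a baseline well and already carries a one-month recall, so using it at Visits 1 and 5 would match the windows. That may well be the intention, but nothing in the documents says so, and section 9.5 requires conduct exactly as described. What stands is that the repair is small.

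The attribution sentence can also be defended. It is prespecified and counts against PAE, so it is conservative for the aim in 2.2. Deleting it would not change a table of any adverse event. That stands. The one-month figure in 8.3 concerns minor complications, a separate descriptive outcome, and does not contradict the test.

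A reader might infer two stronger things. One is that every man would be coded as event-free before PAE, so that six men with a later event give p = 2 × 0.5⁶ = 0.031 against PAE whatever the truth. The plan states no such coding; a missing baseline would ordinarily mean no pair. Even under that coding, the chance of six or more events among 30 men runs from 0.2% (N=0.044) to 19% (N=0.131). The other is that a one-month before window is set against a cumulative three-month after window. Section 2.3.2 does not say that its three months is cumulative, and with persistent symptoms such a mismatch would produce no gap.

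**Conclusion.** The plan is wrong as written and should be fixed before enrolment. The paired test has no planned pre-PAE value, so the adverse-event aim in 2.2 cannot be answered from the scheduled data. This rests on the 4.3 table and the visit descriptions and needs no assumed rate. It would fall away only if the unreproduced medication history form asks about side effects, which the documents do not say.

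The unstated windows and the overlap with medication are secondary. A post window ending at Visit 5 can include drug side effects and so biases the comparison against PAE. The percentages above show direction and sensitivity; they are not estimates for this trial.

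The point does not reach the primary IPSS endpoint, and the aim is secondary and unpowered, so it does not invalidate the trial.

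**What to change.** 1. In the 4.3 table and the visit text, add the 12.2 checklist before PAE at Visit 1 or Visit 2, and use the same checklist after PAE. Add urinary retention and rectal pain: section 5.4 lists both among the common PAE events, and leaving them out would favour PAE.
2. State the same one-month recall for both halves of the McNemar pair and name the post-PAE visit used. Record the trade-off: Visit 5 can overlap medication, and Visit 6 lies further from early procedural events. Since a one-month window at either visit misses the first weeks, report early events descriptively, with 95% confidence intervals, for all treated patients. Say whether the three months in 2.3.2 is cumulative.
3. Keep the test as any listed symptom on both sides. Do not replace the attribution sentence with procedure-relatedness on the post-PAE side alone. The relatedness assessment in 9.3.1 can be reported descriptively.
4. Record medication status at the post-PAE assessment. Add a sensitivity analysis without men still on medication, as 8.3 does for IPSS. It is a sensitivity analysis only, because it drops the men who could not stop.

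Cost: one extra one-page form at an existing visit, two added items, one sensitivity analysis and edited text. No new visit or procedure is needed. Early-event estimates will stay imprecise: 4 of 30 (13%) has an exact 95% interval of 3.8% to 30.7%.
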